### **7.3.1 Diarrhea Occurring Before Addition of MGA012 to MGD007 or Early (within 72 Hours) After Administration of the MGD007/MGA012 Combination**

- Grade 1 diarrhea - Closely monitor the diarrhea until resolution
- Grade 2 diarrhea:
  - Bowel rest
  - Supplemental IV fluids when necessary with close monitoring of fluid and electrolyte status
  - Tocilizumab (anti IL6 receptor) administered as a single 8 mg/kg IV dose. Repeat dosing of tocilizumab may occur after each MGD007 dosing.
  - Monitoring of frequency of bowel movements and stool guaiac
  - For patients unresponsive to tocilizumab (which should be given first), implementation of additional immune suppression consisting of IV corticosteroids using solumedrol at a dosage of 2 mg/kg/day divided twice daily. As tolerated, patients may be converted to oral corticosteroids (i.e., prednisone 2 mg/kg/day divided twice daily) and tapered as appropriate and guided by the patients' clinical status.
- Grade 3 diarrhea (or Grade 2 diarrhea with blood)
  - Hold both MGD007 and MGA012
  - Hospitalize promptly for further evaluation and management
  - Bowel rest
  - Supplemental IV fluids with close monitoring of fluid and electrolyte status
  - Tocilizumab 8 mg/kg IV
  - Monitoring of frequency of bowel movements and stool guaiac
  - For patients unresponsive to tocilizumab (which should be given first), implementation of additional immune suppression consisting of IV corticosteroids using solumedrol at a dosage of 2 mg/kg/day divided twice daily. As tolerated, patients may be converted to oral corticosteroids (i.e., prednisone 2 mg/kg/day divided twice daily) and tapered as appropriate guided by the patients' clinical status.
  - Stool characterization tests should be performed
  - Imaging to rule out bowel obstruction or perforation

- Consideration of colonoscopy as appropriate
- For patients with severe colitis, or those who do not respond to tocilizumab or corticosteroids, additional immune suppression with anti TNF-alpha antibodies (i.e., infliximab) should be considered early in the course
- For patients with Grade 3 diarrhea that lasts less than 48 hours and responds to medical intervention, treatment may be resumed after resolution of the diarrhea to Grade 1 or less in severity within 14 days.
- Grade 4 diarrhea: discontinue MGD007 and MGA012 and treat as for Grade 3 diarrhea. MGD007 and MGA012 should be permanently discontinued.

### **7.3.2 Diarrhea with Onset > than 72 Hours After Administration of the Combination of MGD007/MGA012 or Clinical Manifestations Suggestive of Colitis**

- Grade 1 diarrhea - Closely monitor the diarrhea until resolution.
- Grade 2 diarrhea - Increase frequency of monitoring until resolution. For management of symptoms:
  - loperamide/diphenoxylate
  - low-dose steroids if clinically indicated.
  - Consider management as per Grade 3 diarrhea with prolonged Grade 2 event lasting more than 5 to 7 days or relapsed diarrhea.
- Grade 3 diarrhea - Hold both MGD007 and MGA012. Hospitalize patient promptly for further evaluation and management including:
  - Bowel rest
  - Supplemental IV fluids with close monitoring of fluid and electrolyte status.
  - Monitor frequency of bowel movements
  - Consider imaging to rule out bowel obstruction or perforation
  - Consideration of colonoscopy as appropriate
  - Implementation of initial empiric immune suppression consisting of IV corticosteroids using methylprednisolone at a dosage of 2 mg/kg/day (or equivalent) divided twice daily. As tolerated, patients may be converted to oral corticosteroids (i.e., prednisone 2 mg/kg/day divided twice daily) and tapered as appropriate and guided by the patients' clinical status.
  - Taper corticosteroids as clinically indicated

- For patients with severe colitis, or those who do not respond to corticosteroids, additional immune suppression with anti TNF-alpha antibodies (i.e., infliximab) should be considered early in the course.
- May consider restarting MGD007 and MGA012 if it is determined that there is no colitis, or an alternative cause of diarrhea is found, **and** diarrhea resolves to  $\leq$  Grade 1 within 14 days
- Grade 4 diarrhea-discontinue MGD007 and MGA012 and treat as for Grade 3. MGD007 and MGA012 should be permanently discontinued.

If the etiology of the diarrhea is uncertain, tocilizumab administration also can be considered, in the case of Grade 2 or greater diarrhea at the discretion of the Investigator, in consultation with the Sponsor.

## 7.4 Nausea/Emesis

Based on observations from nonclinical and the clinical experience to date, there is some risk that patients may experience nausea and/or vomiting in conjunction with MGD007 treatment. It is recommended that patients be treated prophylactically with antiemetics in conjunction with the first and subsequent doses of MGD007 ([Section 7.1](#)). For those patients who do experience nausea and/or vomiting after initial dosing, antiemetics should be given as clinically appropriate and consistent with institutional practice. Acceptable antiemetics include but are not limited to serotonin 5-HT3 receptor antagonists, neurokinin 1 receptor antagonists, prochlorperazine, and diphenhydramine. Patients with Grade 2 vomiting despite the specified pre-medication regimen should be promptly managed with a one-time dose of tocilizumab (anti-IL6 receptor) 8 mg/kg IV. Repeat dosing of tocilizumab may occur after each MGD007 dosing. If toxicities are not controlled with tocilizumab, systemic steroids and/or other measures as clinically indicated are recommended. Rehydration with oral or IV supplemental fluids should also be considered.

## 7.5 Immune-Related Adverse Events

Blockade of immune checkpoints (PD-1, PD-L1 and CTLA-4) has been associated with several immune mediated adverse events that develop as a result of disruption of immune tolerance in normal tissues ([18](#), [36](#), [43](#)). These include but are not limited to pneumonitis, autoimmune hepatitis, glomerulonephritis, central neurotoxicity (encephalitis), peripheral neuromuscular toxicity, diarrhea or colitis (discussed in [Section 7.3](#)), hypophysitis, thyroiditis, or other autoimmune endocrinopathies (e.g., pancreatitis and diabetes), myocarditis, and Stevens Johnson Syndrome/Toxic Epidermal Necrolysis. These IrAEs can occur late and require a prolonged follow up. The occurrence of any of these may dictate interruption and potentially discontinuation of study drug administration pending further evaluation and reporting them to the Sponsor as AESIs. Most low-grade immune-related AEs (irAEs) can be managed symptomatically. Persistent low-grade or moderate toxicities may require treatment with corticosteroids or in refractory cases other immune suppressing agents such as

mycophenolate or infliximab. High-grade immune-related toxicities will, in almost all cases, require treatment with high-dose corticosteroids.

Temporary interruptions of the study drugs may be required in the event of treatment-related, immune-related toxicity. General guidelines for specific toxicity regarding dosing and treatment are provided below. All toxicities will be graded according to NCI CTCAE v4.03.

Patients who receive corticosteroid therapy for  $\geq 4$  weeks at a dose equivalent to  $\geq 20$  mg of prednisone per day, consideration should be given to implementation of antibiotic prophylaxis for opportunistic infections.

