#### 8.1.1 Prohibited Therapy

The following rules concerning concurrent treatment(s) will apply in this study:

- Any other anti-neoplastic therapies including but not limited to chemotherapy or other small molecules, biologics, or radiotherapy are not allowed.
  - For patients who require palliative radiotherapy (i.e., cumulative dose less than 30 Gy, limited field of distribution) for reasons other than disease progression, therapy may be interrupted for up to 4 weeks. Palliative radiotherapy may not be given concurrently with the study drug. Treatment with palliative therapy should be initiated at least 24 hours after receiving study drug, and reinitiation can begin 2 weeks after the completion of palliative radiotherapy. If palliative radiotherapy fields overlap tumor lesions that are designated target lesions, the patient may continue on study, but will no longer be evaluable for objective response from the time palliative radiotherapy is initiated.
- Patients may not receive other investigational drugs during the period of study participation.
- The use of other immunosuppressive agents is prohibited unless they are being used to treat an AE.
- Prophylactic use of granulocyte colony stimulating factor, granulocyte-macrophage colony stimulating factor, or other growth factors is prohibited.
- Patients should not receive vaccination with any live virus vaccine during the study and for 120 days following a patient's last dose of MGA012 or of MGD007. Inactivated annual influenza vaccination is allowed.
- Because both MGD007 and MGA012 employs a mechanism of action dependent upon the engagement of T lymphocytes, the use of corticosteroids should be limited to the extent possible. Chronic doses of corticosteroids in excess of 10 mg daily of prednisone or equivalent is prohibited other than for the management of drug-related adverse experiences. Steroids may be employed in the treatment of suspected MGD007- and MGA012-associated autoimmune AEs in consultation with the Sponsor. Specifically, use of budesonide is required with MGD007 dosing per schedule outlined in [Section 7.1](#).

- Use of biphosphonates or RANK-L inhibitors is prohibited.
- Concomitant use of CYP450 substrates with a narrow therapeutic index should be avoided.

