## 9.11 End of Treatment Visit

A list of evaluations to be performed for the EOTV is provided in [Appendix 1](#); a CT or MRI Scan should be performed during the EOTV, unless a previous scan was performed < 28 days of the EOTV. Criteria for triggering the End of Treatment visit are specified in [Section 5.4](#).

The End of Treatment Visit should be performed after the patient has met off-study criteria. This visit should occur no later than 30 days since the last study dose and before any subsequent anti-cancer treatment. If EOTV < 30 days since the last study dose, the site should contact the patient for safety follow-up no later than 30 days after the last study dose (see [Section 12](#)). It is recognized that certain patients (such as those experiencing progression of disease) may be cared for in facilities other than the participating study site, may proceed to receive other cancer therapy, and/or may elect not to return to the study site. Therefore, this visit is considered optional, but should be carried out whenever possible. All required procedures and tests should be performed if a visit is performed.

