## 9.12 Post-treatment Follow-Up Visits

The post-treatment follow-up period includes the following:

- Survival follow-up: approximately a 2-year period for each patient following the last dose of any study drug.
- During this time, patients will be followed via telephone or other electronic contact at 3-month intervals for follow-up of OS.
- Response status: will be collected every 3 months on all patients who discontinued from study treatment due to reasons other than PD, if they have not initiated any other cancer-directed therapy.

Post-treatment follow-up is performed until the end of study for each patient.

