## **12 ADVERSE EVENT REPORTING AND ASSESSMENT OF SAFETY**

The safety assessment will be based on the evaluation of AEs that occur from the time of initiation of administration of study drug through the End of Treatment Visit or 30 days after the last dose of study drug (whichever is later) and will be determined based on signs, symptoms, physical examination findings, and/or laboratory test results from enrolled patients, as appropriate.

Protocol-related AEs and SAEs will be collected from the time the patient has consented to study participation. AEs and SAEs reported between the time the patient signs the informed consent form and the administration of the first dose of study drug will be captured as medical history unless the events are attributed to protocol-specified procedures that are not part of standard of care that occur during this time period, in which case the events will be collected on the SAE Form (as appropriate) and the Adverse Event CRFs.

SAEs considered related to study drug may be reported at any time, even after the patient's final visit.

Progression of the underlying neoplasm resulting in hospitalization or death (e.g., patient hospitalized for or dies from progressive disease [PD] only, without any other SAE) will be documented as an antitumor activity outcome and not as an SAE. If an SAE occurs in a patient and it is unclear whether the event is related to PD, the SAE should be reported.

- A laboratory abnormality should be reported as an AE if it is associated with an intervention. An intervention includes, but is not limited to, discontinuation of treatment, dose reduction/delay, or concomitant therapy. In addition, any medical important laboratory abnormality may be reported as an AE at the discretion of the investigator. This includes laboratory abnormalities for which there are no interventions but the abnormal value(s) suggests a disease or organ toxicity. If clinical sequelae are associated with a laboratory abnormality, the diagnosis or medical condition should be reported (e.g., renal failure, hematuria) not the laboratory abnormality (e.g., elevated creatinine, Urine RBC increased).

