## **12.2 Adverse Event Collection and Documentation**

### **12.2.1 All Adverse Events**

All patients who receive at least one dose of study drug will be considered evaluable for safety. AEs will be determined based on signs, symptoms, physical examination findings, and/or laboratory test results from enrolled patients as appropriate.

All adverse events whether serious or non-serious, will be reported from the time a signed and dated ICF is obtained until 30 days following the last dose of study drug or until the start of a subsequent systemic anti-cancer therapy, if earlier.

Both protocol-related AEs and SAEs will be collected from the time the patient has consented to study participation. AEs and SAEs reported between the time the patient signs the informed consent form and the administration of the first dose of study drug will be captured as concurrent medical history unless the events are attributed to protocol-specified procedures. Events attributed to protocol-specified procedures will be collected on the Adverse Event eCRFs and Serious Adverse Event form as appropriate.

All adverse events, regardless of seriousness, severity, or presumed relationship to study drug, must be recorded using medical terminology in the source document and the eCRF. All records will need to capture:

- The details of the duration, severity, and seriousness of each adverse event,
- the action taken with respect to the study drug(s),
- the investigator's attribution/causality assessment concerning the relationship of the adverse event to study therapy,
- the outcome of the event.

Whenever possible, diagnoses should be given when signs and symptoms are due to a common etiology (e.g. cough, runny nose, sneezing, sore throat, and head congestion should be reported as "upper respiratory infection"). All treatment measures that are required for adverse event management must be recorded in the source document. The intensity (severity) of adverse events will be assessed using NCI CTCAE (Version 4.03) and serious events will

be determined by the definition provided in [Section 12.1.5](#) above. Generally, all non-serious AEs should be entered into the eCRFs within 5 business days of the sites awareness.

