### **12.2.3 Serious Adverse Events**

All SAEs occurring during the study must be reported to the Sponsor.

After 30 days following the last dose of study drug administration, only SAEs the Investigator believes considered related to study drug or a protocol procedure, should be reported to the Sponsor.

Information regarding SAEs will be transmitted to the Sponsor using the Serious Adverse Event Form, which must be completed and signed by a physician from the study site and transmitted to the Sponsor within 24 hours of the site becoming aware of the serious adverse event. The initial and follow-up serious adverse reports should be scanned and emailed or transmitted by facsimile (fax) to the Sponsor.

All Grade 3 or Grade 4 SAEs considered related to study drug must be followed until recovery to baseline or Grade 1.

The Investigator must follow all SAEs until resolution and record the date of resolution. Resolution of an event is defined as the return to pre-treatment status or stabilization of the condition with the expectation that it will remain chronic.

All SAEs that have not resolved by the end of the study, or that have not resolved upon discontinuation of the patient's participation in the study, must be followed until any of the following occurs:

- The event resolves.
- The event stabilizes.
- The event returns to baseline, if a baseline value/status is available.

- The event can be attributed to etiology other than the study drug or to factors unrelated to study conduct.
- It becomes unlikely that any additional information can be obtained (patient or health care practitioner refusal to provide additional information, lost to follow-up after demonstration of due diligence with follow-up efforts).

Any event requiring hospitalization (or prolongation of hospitalization) that occurs during the course of a patient's participation in a study must be reported as a SAE, except hospitalizations for the following:

- A standard hospitalization for administration of study drug therapy will not be reported as a serious adverse event.
- A procedure for protocol/disease-related investigations (e.g., surgery, scans, endoscopy, sampling for laboratory tests, bone marrow sampling, pharmacokinetic or biomarker blood sampling).
- Hospitalizations not intended to treat an acute illness or adverse event (e.g., social reasons such as pending placement in long-term care or hospice facility).

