5.2 Safety Endpoints

5.2.1 Adverse Events

Adverse event (AE) means any untoward medical occurrence in a patient or clinical trial patient associated with the use of a drug in humans, whether or not considered drug related. An adverse event can therefore be any unfavorable and unintended sign (including an abnormal laboratory finding, for example), symptom, or disease temporally associated with the use of a medicinal product, whether or not considered related to the medicinal product.

AEs will be captured starting from date of first study drug through end of treatment visit or 30 days following last dose of study drug (whichever is later). Only treatment-related serious AEs will be captured afterwards. These events will be recorded by the Investigators in the eCRFs. Verbatim terms will be coded to lower-level terms using the most recent version of the Medical Dictionary for Regulatory Activities (MedDRA). An assessment of severity grade will be made using National Cancer Institute-Common Terminology Criteria for Adverse Events (NCI-CTCAE) Version 4.03.

AEs reported between the time the patient signs the informed consent form and the administration of the first dose of study drug will be captured as medical history unless the AE is attributable to protocol-specified procedures that are not part of standard of care that occur during this time period, in which case the AE will be collected as AEs on the Adverse Event CRFs. Only treatment emergent adverse events (TEAEs) will be summarized in tables. A TEAE is defined as any event that is newly occurring on or after the administration of

study drug or an event that existed before but increased in severity on or after study drug administration.

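### Late non-serious immune-related AEs have no collection route after day 30, although the protocol says such events need prolonged follow-up

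*Protocol*

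**What the plan says.** **The stated need.** Protocol 7.5 lists irAEs seen with checkpoint blockade, says "These IrAEs can occur late and require a prolonged follow up", and has them reported to the sponsor as AESIs. Section 12.2.4 names the Grade 2 or greater events concerned (among them colitis, pneumonitis, hepatitis, nephritis, hypophysitis and thyroid disorders). It requires notification whether or not they are serious, and gives no end date of its own.

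**The collection window.** Section 12.2.1 collects all AEs, serious or not, "until 30 days following the last dose of study drug or until the start of a subsequent systemic anti-cancer therapy, if earlier". The opening of Section 12 says instead "through the End of Treatment Visit or 30 days after the last dose of study drug (whichever is later", and SAP 5.2.1 follows that form. For the End of Treatment Visit, Section 9.11 says "This visit should occur no later than 30 days since the last study dose", and also treats the visit as optional.

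**After the window.** Section 12.2.3: "After 30 days following the last dose of study drug administration, only SAEs the Investigator believes considered related to study drug", or to a protocol procedure, are reported. SAP 5.2.1: "Only treatment-related serious AEs will be captured afterwards".

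**Contacts that already exist.** Section 9.12: "patients will be followed via telephone or other electronic contact at 3-month intervals for follow-up of OS", for about 2 years. Response status is also gathered in patients who stopped for reasons other than progression and have had no other cancer therapy. Neither Section 9.12 nor Appendix 1 includes a question about irAEs.

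**The output.** Protocol 14.7.1 and SAP 6.7.1 plan a summary table of AESIs.

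**The concern.** The protocol says that irAEs may come late and need long follow-up, and it defines a set of them as being of special interest whatever their seriousness. Its collection rules then close for non-serious events at about day 30. An AESI table built under those rules would show non-serious irAEs up to roughly day 30 and only related serious ones after it, and nothing in the table would tell the reader that ascertainment changed. In a Phase 1b/2 study that adds an anti-PD-1 antibody to a T-cell engager, the irAE profile is part of what the safety tables are meant to describe. Patients are already being contacted every 3 months, so the gap arises from what is asked at those contacts and not from a lack of contact.

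**Working it through.** The plan has no figure of its own to reproduce here. The check sets the rules side by side, followed by a supporting calculation on residual drug.

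**1. Follow one event through the rules.** Take a Grade 2 hypothyroidism judged immune-mediated, diagnosed 45 days after the last dose, treated as an outpatient and not serious.

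- Section 12.2.4: it is an AESI by type and grade, and seriousness does not matter. No time window is given, and no visit or contact is assigned to find it.
- Section 12.2.1: outside the window (45 > 30 days).
- Section 12: the End of Treatment Visit is due by day 30, so taking the later of the visit and day 30 still gives day 30 when the visit is on schedule. Outside.
- Section 12.2.3 and SAP 5.2.1: not serious, so not taken.
- Section 9.12: the next contact asks about survival and, in some patients, response.

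The event has no collection route. The SAP's definition of a treatment-emergent AE has no end date, so the event would enter the AESI table if it were collected. The gap is in collection, not in tabulation.

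**2. The window itself is stated in two ways.** Suppose new systemic therapy starts on day 10. Under Section 12.2.1 collection stops on day 10. Under the opening of Section 12 and SAP 5.2.1 it runs to day 30. An event on day 20 is collected under one rule and not under the other, so the passages must be reconciled.

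**3. Contacts available.** 24 months / 3 months = 8 contacts per patient who completes follow-up. The first falls about 90 days after the last dose.

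**4. Residual MGA012 at day 30 (rough plausibility only).** Inputs: mean half-life 408.9 h with SD 282.6 h (Protocol 2.6.2.1, Table 6), and predicted steady-state peak and trough for 3 mg/kg every 2 weeks of 86.6 and 23.6 µg/mL (Table 7).

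- Single-exponential decline from peak: 0.5^(30 × 24 / 408.9) = 0.5^1.76 = 0.295, about 30%.
- The same formula at day 14 gives 0.5^(336 / 408.9) = 0.57, but Table 7 implies 23.6 / 86.6 = 0.27. The single-exponential shortcut therefore overstates serum concentration after the early phase.
- Starting from the Table 7 trough and applying the half-life for the remaining 16 days: 0.27 × 0.5^(384 / 408.9) = 0.27 × 0.52 = 0.14, about 14% of peak.
- First formula with the half-life one SD either side: at 126.3 h, 0.5^(720 / 126.3) = 0.02; at 691.5 h, 0.5^(720 / 691.5) = 0.49.

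A fair statement is about 14% to 30% at day 30 depending on the decline assumed, and about 2% to 49% once half-life variability is allowed for. Table 7 rests on 5 patients at this dose. These percentages say that some drug is plausibly present. They do not say how many irAEs are missed.

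**The case against.** **Late may mean late in treatment.** The text after the Section 7.5 sentence concerns interrupting or stopping study drug, and treatment can last about 2 years with continuous AE assessment. This is a fair reading of part of the sentence, but it does not account for the call for prolonged follow-up. A reader might infer a flat contradiction between Section 7.5 and Section 12.2.1. The documents do not go that far, because Section 7.5 sets no post-treatment window.

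**The important late events are covered.** This stands. Related SAEs may be reported at any time (Sections 12 and 12.2.2), and the SAE definition in Section 12.1.5 includes important medical events, so a significant Grade 3 hepatic or pituitary event can qualify without admission. A reader might infer that late irAEs are lost altogether. They are not: the gap is confined to non-serious ones.

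**Section 12.2.4 has no end date.** It could be read as open-ended. But nothing in it overrides Section 12.2.1 or SAP 5.2.1, and no contact is assigned to ask. At best the text is ambiguous, which also calls for an edit.

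**Other windows in the protocol are longer.** Section 8.1.1 bars live vaccines "for 120 days following a patient's last dose of MGA012 or of MGD007", and the contraception criteria also use 120 days. A reader might take this as the protocol's own view of how long AEs should be collected. These are precautions with a different purpose and set no AE window.

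**A telephone question finds little.** In part this stands. Hepatic and thyroid events are often recognised from laboratory results, Appendix 1 schedules no safety laboratory tests after the End of Treatment Visit, and some patients will be treated elsewhere. The question would find diagnosed or treated events and miss silent ones.

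**No objective names AESI incidence, and the protocol's AESI table is qualified as if applicable.** This is true and keeps the priority low. Safety is nonetheless an objective of both phases, and SAP 6.7.1 lists the AESI table without that qualifier.

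**Conclusion.** The point holds in a limited form. Non-serious irAEs with onset after about day 30, or after the start of new systemic therapy if Section 12.2.1 governs, have no collection route and would be missing from the AESI table. Related serious irAEs are not affected.

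The direction of the effect is an understatement of late non-serious irAEs. Its size cannot be computed, because the documents give no late-onset irAE rate. A reader might infer from the half-life that about 30% of MGA012 remains at day 30 and treat that as a measure of the loss. The documents do not support this: the figure depends on the decline assumed (about 14% from Table 7), varies widely between patients, and is not an event rate. It is best left out or given only as a rough range.

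The conclusion assumes that Section 12.2.1 and SAP 5.2.1 govern what is entered in the database and that Section 12.2.4 does not silently extend them. This is a low-priority, inexpensive improvement. The disagreement between Section 12.2.1 and Section 12 over when the window closes should be settled in the same edit.

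**What to change.** - State a window of about 90 days after the last dose for the immune-related AESIs listed in Section 12.2.4, serious or not. Say that it continues after subsequent anti-cancer therapy starts.
- At the first scheduled 3-month contact, ask about these events. Record the onset date, grade, causality assessment for each study drug, and the start date of any subsequent anti-cancer therapy.
- In the AESI table, show events with onset after day 30 separately, with the number of patients actually reached at that contact. Add a note that asymptomatic laboratory changes were not sought after the End of Treatment Visit.
- Amend Protocol Section 12, 12.2.1, 12.2.3, 12.2.4, 9.12 and Appendix 1 together with SAP 5.2.1. Section 12.2.1 must be included because it holds the operative cut-off.
- In the same amendment, choose one closing rule for general AE collection and use it in Section 12, Section 12.2.1 and SAP 5.2.1.

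The cost is one question at a contact that already takes place and modest data entry, with no new visit or test. The downside is incomplete and somewhat uneven ascertainment after day 30, which is why those events should be labelled as such.
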